### **9.1.1. Incidence of Adverse Events**

All AEs will be summarized for the Safety Set in the manner described in Section 9. Counts and percentage of patients with each type of AE will be provided. Denominators for percentages will be the total number of patients treated in each arm or overall. At each level of patient summarization, a patient is counted once if the patient reported one or more events.

An overview summary of the number and percentage of patients with any TEAE, serious TEAE, study drug-related TEAE, study drug-related serious TEAE, TEAE leading to treatment discontinuation, TEAE leading to study discontinuation, and AE leading to death will be provided by treatment arm.

Treatment-emergent AEs will also be summarized separately for each injection cycle for BOTOX treated patients.

The following summary tables will be repeated for any TEAE, serious TEAE, study drug-related TEAE, study drug-related serious TEAE, TEAE leading to treatment discontinuation, TEAE leading to study termination, and AE leading to death.

Summaries of the total number of TEAEs and the number and percentage of patients with at least one TEAE will be provided by treatment group. The number and percentage of patients and the number of events will also be presented by SOC and PT in descending order from the SOC with the highest total incidence (that is, summed across all treatment groups) to the SOC with the lowest total incidence. If the total incidence for any 2 or more SOCs is equal, the SOCs will be presented in alphabetical order. Within each SOC, the PTs will be presented in alphabetical order. At each level of patient summarization, a patient is counted once if the patient reported one or more events.

All AEs, will be presented in a by-patient listing.

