5.4.2.2 Dose Maintenance

Starting at week 4 (ie, the maintenance phase), the patient should remain on a stable topiramate dose of at least 50 mg/day. As per the recommended topiramate dose for migraine prophylaxis, the topiramate dose must not exceed 100 mg/day ([Topamax[®] US package insert, 2012](#)). At the next scheduled office visit (ie, week 12), the investigator, at

his/her discretion, may adjust the topiramate dose (upward or downward) to be within the range of 50 to 100 mg/day; the patient should remain on this dose for the remainder of topiramate treatment in the study.

For all patients who complete topiramate treatment or who discontinue from treatment, a dose taper period of up to 2 weeks is recommended. The investigator will determine the duration of the taper, which is based on the maximum dose received during the maintenance phase.

Patients who discontinue topiramate at any time up to or including week 36 will crossover to receive treatment with BOTOX 155 U for the remainder of the study. The first BOTOX treatment will be administered at the next scheduled office visit, and the patient will return every 12 weeks up to and including the week 36 visit to receive BOTOX treatments, with a final exit visit at week 48. BOTOX treatment can be initiated during the topiramate dose tapering period.

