## 4. General Statistical Considerations

Continuous data will be summarized using descriptive statistics (ie, n, mean, standard deviation [SD], median, minimum, and maximum). Categorical data will be summarized using the patient count and percentage in each category. Confidence intervals (CIs) will be 95% and 2-sided, unless otherwise stated. Data will be displayed in all listings sorted by treatment group and patient number. P-values will be rounded to three decimal places. If a p-value is less than 0.001 it will be reported as “<0.001.” If a p-value is greater than 0.999 it will be reported as “>0.999.” Data will be displayed in all listings sorted by treatment group.

Patients will be identified in the listings by the patient identification number concatenated with the investigator number.

When count data are presented, the percentage will be suppressed when the count is zero in order to draw attention to the nonzero counts. A row denoted “Missing” will be included in count tabulations specified on the shells to account for dropouts and missing values. The denominator for all percentages will be the number of patients in that treatment group within the analysis set of interest, unless otherwise specified. Nonzero percentages will be rounded to one decimal place, except 100%, which will be displayed without any decimal places. Additional rounding rules are as follows:

- If the original value has 0 decimal places: mean, median, and CIs will have one decimal place and SD will have 2 decimal places
- If the original value has 1 decimal place: mean, median, and CIs will have 2 decimal places and SD will have 3 decimal places
- If the original value has 2 or more decimal places: mean, median, CIs, and SD will all have 3 decimal places

Minimum and maximum will always have the same decimal places as the original value, up to a maximum of 3 decimal places.

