#### **4.3.4. Safety**

The Safety Set will include all patients who received at least one dose of study drug.

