## 9. Safety Analyses

All analyses of safety will be conducted using the Safety Set. All patients will be summarized according to the treatment they actually received, but the subgroup of topiramate patients who initially received topiramate and then switched to BOTOX will be summarized as follows:

- All safety assessments occurring prior to the date of the first dose of BOTOX will be summarized for the topiramate treatment arm.
- All safety assessments except AEs occurring on or after the date of the first dose of BOTOX will be summarized separately for the topiramate + BOTOX subgroup. For all AEs, the total number of patients (N) in each treatment arm will represent the number of patients that received that treatment. A patient may be counted in both treatment arms. The overall total will be the number of patients that received any treatment. The topiramate + BOTOX treatment arm will be a subset of the BOTOX treatment arm and will include patients that received both treatments. Denominators for percentages will be the total number of patients in each treatment arm or overall. Treatment-emergent AEs (TEAEs) include all AEs that start on or after the first dose of study medication up to the final visit, or are present prior to the first dose but increase in severity after the first dose of study medication up to the final visit. For patients who switch from topiramate to BOTOX, TEAEs starting on or after the date of the first BOTOX injection will be counted in the treatment arm that they are related to, as determined by a physician. If the TEAE is related to both treatments or if the relationship is unknown, it will be counted in both treatment arms but only once in the total. The topiramate + BOTOX subset will summarize all TEAEs that occurred after a patient has switched from topiramate to BOTOX.

Statistical hypothesis testing will not be performed on any safety results

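### SAP 9.1.1 sets no denominator for the adverse-event tables by BOTOX injection cycle, and the rules that apply by default count patients who never received the later injections

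*SAP*

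**What the plan says.** - SAP 9.1.1 announces the table: "Treatment-emergent AEs will also be summarized separately for each injection cycle for BOTOX treated patients". The sentence carries no denominator of its own.
- The only denominator rule in that section is: "Denominators for percentages will be the total number of patients treated in each arm or overall".
- SAP 9 sets the N for every adverse-event table: "For all AEs, the total number of patients (N) in each treatment arm will represent the number of patients that received that treatment". It also places the switchers inside BOTOX: "The topiramate + BOTOX treatment arm will be a subset of the BOTOX treatment arm and will include patients that received both treatments".
- SAP 4 gives the general default: "The denominator for all percentages will be the number of patients in that treatment group within the analysis set of interest, unless otherwise specified". Nothing else is specified for cycles. SAP 4.3.4 requires one dose only: "The Safety Set will include all patients who received at least one dose of study drug".
- Protocol 5.4.2.2 fixes when switchers are injected: "The first BOTOX treatment will be administered at the next scheduled office visit, and the patient will return every 12 weeks up to and including". Week 36 is the last such visit. Protocol 8.8 and SAP 7.2 give the possible switch visits as Weeks 12, 24 and 36, and both say that a patient who stops BOTOX leaves the study.
- SAP 9 counts treatment-emergent events up to the final visit, whereas SAP 9.1 stops before the Week 36 office visit. A switcher's final visit is at Week 48.

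**The concern.** An adverse event in cycle 2 or 3 can occur only in a patient who received that injection. The default N keeps patients in the later-cycle denominators who had no chance of an event there: Week 36 switchers (one cycle), Week 24 switchers (at most two) and patients who left after injection 1 or 2.

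A reader will naturally use a cycle table to judge whether adverse events change with repeated injection. SAP 9 rules out hypothesis tests on safety results, so the descriptive percentages are what the reader has. With the default N they would drift downward through the denominator alone, in BOTOX's favour, and partly offset any real increase.

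**Working it through.** **Plan's own figure.** The plan states no adverse-event, dropout or switching rate, so the only figure to reproduce is the arm size. For 28% against 44%, two-sided 0.05 and 90% power, the uncorrected formula gives 188 per arm and the continuity-corrected one gives 200, as stated (power 90.1%). I use 200 per arm.

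**Formula.** Let p be a constant rate per injection, n_k the number who received injection k, and N all BOTOX-treated patients. The table shows p × n_k / N. With r2 and r3 the shares of randomised BOTOX patients receiving injections 2 and 3, and s12, s24, s36 the switchers by visit of first injection:

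- N = n_1 = 200 + s12 + s24 + s36
- n_2 = 200 r2 + s12 + s24
- n_3 = 200 r3 + s12

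**Inputs (all assumptions).**

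- Set A: r3 = 539/688 = 78.3%, the share evaluable at Week 24 in the earlier phase 3 studies (SAP 4.1), used as a proxy; r2 = 89%, an assumed midpoint. Switchers S = 28 or 64, that is 14% or 32% of 200, from the non-evaluable fractions in the cited topiramate studies (13/95 and 54/170), spread evenly over the three visits.
- Set B, better retention: r2 = 95%, r3 = 90%; S = 40 or 100 (20% or 50%), split evenly or 50/30/20.

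| Set | N | n_2 (n_2/N) | n_3 (n_3/N) | A constant 10% is shown as |
|---|---|---|---|---|
| A, S = 28 | 228 | 197 (0.863) | 166 (0.728) | 10.0 / 8.6 / 7.3% |
| A, S = 64 | 264 | 221 (0.836) | 178 (0.674) | 10.0 / 8.4 / 6.7% |
| B, S = 40, even | 240 | 217 (0.903) | 193 (0.806) | 10.0 / 9.0 / 8.1% |
| B, S = 100, even | 300 | 257 (0.856) | 213 (0.711) | 10.0 / 8.6 / 7.1% |
| B, S = 40, 50/30/20 | 240 | 222 (0.925) | 200 (0.833) | 10.0 / 9.3 / 8.3% |
| B, S = 100, 50/30/20 | 300 | 270 (0.900) | 230 (0.767) | 10.0 / 9.0 / 7.7% |

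Example, first row: n_3 = 200 × 0.783 + 28/3 = 166, and 166/228 = 0.728. Cycle 3 is understated by 1 − n_3/N, which is 27–33% in set A and 17–29% in set B. The ratio does not depend on p.

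**Sensitivity.**

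- Dropout alone at 95%/90%, with no switchers: 10% in cycle 3.
- Harsher case: r3 = 514/688 = 74.7% and 20% of the topiramate arm switching at each visit. Then N = 320, n_3 = 149.4 + 40 = 189.4, ratio 0.592, understatement 41%.
- Zero only if nobody misses injection 2 or 3, for example no dropout and every switch at Week 12.
- The 32% input comes from an inconsistent source figure. The plan gives 45 responders among n = 170 as 29.4%, but 45/170 = 26.5%, and 29.4% fits 45/153. With 153, the non-evaluable share is 1 − 116/153 = 24%, so S = 48, N = 248, n_3 = 156.7 + 16 = 172.7, ratio 0.696. The upper end moves from 33% to 30%.

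**What is masked.** A true rise is hidden in cycle 3 if it is no larger than N/n_3 − 1: 37–48% in set A (1/0.728 and 1/0.674), 20–41% in set B (1/0.833 and 1/0.711). In set A, a rise from 10% to 13.7–14.8% would print as flat.

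**Week 36 cut-off.** Take r2 = 0.92, r3 = 0.85, switchers 40/20/20 at Weeks 12/24/36, and a constant 30%. Then n_k = 280/244/210. If events after a Week 36 injection are not counted, the patients who can contribute are 260, 224 and 170. Even with n_k as denominator the table shows 30% × 260/280 = 27.9%, 30% × 224/244 = 27.5% and 30% × 170/210 = 24.3%.

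**The case against.** The cycle sentence states no denominator and does not itself mention percentages. The rule earlier in SAP 9.1.1 is written for arms, and a cycle is not an arm. SAP 4 refers to table shells, which are not among the documents and may carry a cycle-specific N. This stands in part. A reader might infer that the table will certainly be divided by all BOTOX patients; the documents do not establish that. They do give three rules that all lead to that N and no exception, so the SAP text needs to settle it.

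The consequence is limited, and this stands. The protocol's tolerability hypothesis concerns the difference between groups. SAP 9.1.1 also plans patient and event counts, and SAP 7.2 plans listings of BOTOX administration by visit, so correct rates could be recovered. The SAP does not state a purpose for the cycle table.

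The inputs are proxies, and this stands too. Being evaluable for response in an earlier study is not the same as receiving injection 3. Being non-evaluable in another topiramate study is not the same as switching: here, loss to follow-up, withdrawn consent, pregnancy and a C-SSRS exit remove patients without a switch.

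The simple formula also leaves out the SAP 9 rule that assigns a switcher's events after the first BOTOX injection to a treatment by physician-judged relationship. Some of those events would leave the BOTOX numerator.

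**Conclusion.** The concern holds as a gap in SAP 9.1.1 whose default filling gives wrong later-cycle percentages. At a constant rate per injection, the direction is certain unless no BOTOX-treated patient misses injection 2 or 3. The size, roughly 17–33% in cycle 3, rests on assumed retention and switching; other plausible assumptions fall outside that range, and the top of it drops to 30% if the inconsistent source figure is read as 153 patients.

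Two stronger readings are tempting and not supported. One is that the comparison of adverse events between BOTOX and topiramate is distorted: the cycle denominators do not enter it. The other is that the table would hide any increase with repeated injection: only rises smaller than the dilution are masked, and larger ones would still show, though reduced.

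The matter is confined to one descriptive table within BOTOX. It is worth correcting because the correction is cheap and the default error runs in one direction.

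**What to change.** In SAP 9.1.1, state that for the injection-cycle tables the denominator for cycle k is the number of patients who received BOTOX injection k, and show that N in the column header. Present patients randomised to BOTOX and topiramate + BOTOX patients separately by cycle, because the mix changes across cycles. SAP 9 already separates the switchers' post-switch events, but not expressly by cycle.

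Reconcile the end of the treatment-emergent period in SAP 9 (final visit) with SAP 9.1 (before Week 36). Otherwise events after a switcher's Week 36 injection are lost while that patient stays in the denominator.

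Add a note that recipients of later injections are a selected group who tolerated the earlier ones; the corrected denominator does not remove that selection.

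The denominator change costs one sentence and new column headers, and the injection records are already collected. The downside is that later-cycle percentages become slightly less favourable to BOTOX.

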### **9.1.2. Relationship of Adverse Events to Study Drug**

A summary of TEAEs by relationship to study drug will be presented in a table by incidence of occurrence. The relationships will be collected as the possibility that study drug caused the event

and will be reported as “Related” or “Not Related”. In the TEAE relationship table, if a patient reports multiple occurrences of the same AE, only the most closely related occurrence will be presented. Treatment-emergent AEs that are missing a relationship will be presented in the summary table as “Related”, but will be presented in the data listing with a missing relationship. Percentages will be calculated by the number of patients in the Safety Set. Denominators for percentages will be the total number of patients treated in each arm or overall.

The TEAE data will be categorized and presented by SOC, PT, and relationship in a manner similar to that described in Section 9.1.1.

### **9.1.3. Severity of Adverse Event**

A summary of TEAEs by severity will be presented in a table. The severity that will be presented represents the most extreme severity captured on the eCRF page. In the TEAE severity table, if a patient reported multiple occurrences of the same TEAE, only the most severe will be presented. Treatment-emergent AEs that are missing severity will be presented in tables as “Severe” but will be presented in the data listing with a missing severity. Counts and percentage of patients within each category will be provided using the Safety Set. Denominators for percentages will be the total number of patients treated in each arm or overall.

A clinical determination will be made of the intensity of an AE. The severity assessment for a clinical adverse event must be completed using the following definitions as guidelines:

- Mild: Awareness of sign or symptom, but easily tolerated.
- Moderate: Discomfort enough to cause interference with usual activity.
- Severe: Incapacitating with inability to work or do usual activity.
- Not applicable: In some cases, an adverse event may be an ‘all or nothing’ finding which cannot be graded.

The AE data will be categorized and presented by SOC, PT, and severity in a manner similar to that described in Section 9.1.1.

### **9.1.4. Serious Adverse Events**

The seriousness of an AE should be assessed by the Investigator independently from the severity of the AE. A serious AE (SAE) is defined as any untoward medical occurrence that, at any dose, results in death, is life-threatening, is a congenital anomaly/birth defect, requires inpatient hospitalization or prolongation of existing hospitalization, or results in a persistent or significant disability/incapacity.

Important medical events that may not result in death, be life-threatening, or require hospitalization may be considered SAEs when, based upon medical judgment, they may jeopardize the patient and may require medical or surgical intervention to prevent one of the outcomes listed above.

The serious TEAE data will be categorized and presented by SOC and PT in a manner similar to that described in Section 9.1.1.

A by-patient listing of SAEs will be presented.

### **9.1.5. Adverse Events Leading to Treatment Discontinuation**

A summary of TEAEs with a study drug action taken of either “Drug Withdrawn” or “Switched to BOTOX” will be presented in a table. At each level of patient summarization, a patient is counted once if the patient reported one or more events. Counts and percentage of patients within each category will be provided. Denominators for percentages will be the total number of patients treated in each arm or overall.

Treatment-emergent AEs leading to treatment discontinuation will be categorized and presented by SOC and PT in a manner similar to that described in Section 9.1.1.

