2.2 Clinical Hypotheses

[figure not shown]
- BOTOX is more effective than topiramate as measured by the difference between treatment groups in a 50% responder rate (defined as the proportion of patients with a $\geq 50\%$ reduction from baseline in the number of headache days over a 28-day period).
- BOTOX has a superior tolerability profile than topiramate as measured by the difference between treatment groups in the rates of adverse events and discontinuations due to adverse events.
- BOTOX has an acceptable safety profile.

3. Study Design

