Patients randomized to receive topiramate treatment will receive up to 36 weeks of daily topiramate treatment. A stable topiramate dose of at least 50 mg/day is required (maximum 100 mg/day) (see Section 5.4.2 for details). The final/exit visit for patients who complete topiramate treatment will be at week 36. Patients who discontinue topiramate treatment before the week 36 visit will return to the office approximately every 12 weeks up to and including the week 36 visit to receive BOTOX 155 U, for a maximum of 3 BOTOX treatment sessions in the study. The final/exit visit for these patients who discontinue topiramate and subsequently receive BOTOX will be at week 48 (or approximately 12 weeks after the last injection).

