3.3 Study Treatments

Study medication will be administered for up to 48 weeks. Following a 28-day run-in period, patients meeting the inclusion/exclusion criteria will receive their first treatment on day 1. Patients will be randomized in a 1:1 ratio to receive IM injections of BOTOX 155 U administered approximately every 12 weeks, or topiramate administered orally at doses up to 100 mg/day (minimum 50 mg/day), until week 36. Patients who discontinue topiramate treatment on or before the end of the week 36 visit will crossover to BOTOX treatment for the remainder of the study. All patients receiving BOTOX will be followed for approximately 12 weeks after the last injection.

Patients randomized to receive BOTOX treatment will receive 3 treatment sessions of BOTOX over the course of the treatment period, ie, at day 1, week 12 ± 7 days, and week 24 ± 7 days. During each of the treatment sessions, each patient will receive a dose of 155 U BOTOX administered as 31 fixed-site, fixed-dose IM injections across 7 specific head/neck muscle areas (ie, the US labeled injection paradigm; [BOTOX[®] US package insert, 2013](#)). The follow-the-pain injection paradigm should not be used. Patients who complete BOTOX treatment at week 24 will be exited from the study at the week 36 visit.

Patients randomized to receive topiramate will receive up to 36 weeks of daily treatment. There will be a 4-week titration phase starting on day 1, followed by a dose maintenance phase for the remainder of topiramate treatment. At the day 1 office visit, patients will receive an initial dose of topiramate 25 mg/day and will be instructed to continue this dose for 1 week. Patients will be instructed that, during the next 3 weeks of the titration phase, the topiramate dose should be increased in weekly increments of 25 mg/day until a dose of 100 mg/day (or a lower maximum tolerated dose) is reached. Upon discussion with the investigator, the patient may also decrease the dose until the topiramate dose is optimized. Starting at week 2, topiramate will be administered in 2 divided doses. Starting at week 4 (ie, the maintenance phase), a stable topiramate dose of at least 50 mg/day is required. As per the recommended topiramate dose for migraine prophylaxis, the topiramate dose must

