not exceed 100 mg/day ([Topamax[®] US package insert, 2012](#)). At the next scheduled office visit (ie, week 12), the investigator, at his/her discretion, may adjust the topiramate dose (upward or downward) to be within the range of 50 to 100 mg/day; the patient should remain on this dose for the remainder of topiramate treatment in the study. For all patients completing topiramate treatment or those who discontinue from treatment, a dose taper period of up to 2 weeks is recommended. Refer to Section 5.4.2 for further details.

Patients who complete topiramate treatment at week 36 will be exited from the study at week 36. Patients who discontinue topiramate treatment at any time up to or including week 36 will crossover to receive treatment with BOTOX 155 U for the remainder of the study. The first BOTOX treatment will be administered at the next scheduled office visit, and the patient will return every 12 weeks up to and including the week 36 visit to receive BOTOX treatments, with a final exit visit at week 48. BOTOX treatment can be initiated during the topiramate dose tapering period.

All patients receiving BOTOX in the study will be followed for 12 weeks after the last injection.

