5.7 Treatment Administration

Following a 28-day run-in period, patients meeting the inclusion/exclusion criteria will receive their first treatment at visit 2 (day 1). On day 1, patients will be randomized in a 1:1 ratio to receive IM BOTOX 155 U administered approximately every 12 weeks or up to 100 mg/day oral topiramate administered daily, up to week 36. Patients who discontinue topiramate treatment on or before the week 36 visit will receive treatment with BOTOX for the remainder of the study.

Patients randomized to receive BOTOX treatment will receive 3 treatment sessions of BOTOX according to the US labeled injection paradigm (see Section 5.4.1) over the course of the study, ie, at day 1, week 12 ± 7 days, and week 24 ± 7 days.

Patients randomized to receive topiramate treatment will receive up to 36 weeks of topiramate administered orally at doses starting at 25 mg/day given once daily and tapered up to 100 mg/day given twice daily. Patients will continue to receive daily doses of topiramate until week 36 or early discontinuation (with dose tapering to commence at the time of discontinuation).

Patients who discontinue topiramate treatment prior to week 36 will be asked to return to the office at the next scheduled visit to receive treatment with BOTOX. These patients will receive IM injections of BOTOX 155 U approximately every 12 weeks up to and including the week 36 visit, for a maximum of 3 BOTOX treatment sessions during the course of the study. BOTOX treatment can be initiated during the topiramate dose tapering period.

All patients receiving BOTOX in the study will be followed for approximately 12 weeks after the last injection.

6. Response Measures and Summary of Data Collection Methods

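### SAP 9.1.5 compares AE-related treatment discontinuation without a common window: topiramate can be stopped up to Week 36, but a patient randomised to BOTOX has no dose left to withhold after Week 24

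*SAP*

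**What the plan says.** The second hypothesis in Protocol 2.2 is that BOTOX is better tolerated, as "measured by the difference between treatment groups in the rates of adverse events and discontinuations due to adverse events".

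SAP 9.1.5 supplies the discontinuation measure. It plans "A summary of TEAEs with a study drug action taken of either" *Drug Withdrawn* or *Switched to BOTOX*, and it states that "Denominators for percentages will be the total number of patients treated in each arm or overall". The section sets no cut-off date and makes no adjustment for time at risk.

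The two drugs follow different calendars:

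- **Topiramate.** Protocol 3.1: "Patients randomized to receive topiramate treatment will receive up to 36 weeks of daily topiramate treatment". Protocol 5.7: "Patients will continue to receive daily doses of topiramate until week 36 or early discontinuation". Protocol 3.3: "Patients who discontinue topiramate treatment at any time up to or including week 36 will crossover" to BOTOX.
- **BOTOX, as randomised.** Protocol 3.3 schedules injections at Day 1, Week 12 and Week 24 and adds: "Patients who complete BOTOX treatment at week 24 will be exited from the study at the week 36 visit".

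Four other SAP provisions bear on the reading:

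- Section 9 tabulates AEs as treated, makes the topiramate + BOTOX group a subset of the BOTOX column, and rules out hypothesis tests on safety results.
- Section 9.1 runs the TEAE window to the Week 36 visit.
- Section 7.1 counts BOTOX exposure to 84 days after the last injection.
- Section 9.1.1 also tabulates TEAEs leading to study discontinuation.

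**The concern.** An AE enters the 9.1.5 table only through an action taken on study drug. A topiramate patient can take that action on any day for 36 weeks. A patient randomised to BOTOX has two later doses that can be withheld, at Weeks 12 and 24. If an intolerable AE follows the third injection, there is no scheduled dose to withdraw.

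If such events are not coded as withdrawals, topiramate stops in Weeks 24-36 enter the comparison with no BOTOX counterpart. Part of any difference in favour of BOTOX would then reflect how often each drug is given rather than how well it is tolerated. Because no safety test is planned, these percentages are a main part of what a reader has for the discontinuation half of the tolerability hypothesis.

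**Working it through.** **Plan's own figure.** The documents give no expected AE-discontinuation rate and no time course, so there is no stated figure to reproduce. The sample-size calculation concerns the responder endpoint only.

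**Step 1: time during which a dose can still be withdrawn** (Protocol 3.1, 3.3, 5.7).

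- Topiramate: 36 × 7 = 252 days.
- Randomised BOTOX, to the last injection: 24 × 7 = 168 days.
- Difference: 252 − 168 = 84 days, and 84/252 = 33% of the topiramate period.

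**Step 2: switchers in the BOTOX column** (SAP 9; Protocol 3.3, which allows their injections up to and including Week 36).

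| First BOTOX injection | Later scheduled injections that could be withheld |
|---|---|
| Week 12 | 2 (Weeks 24 and 36) |
| Week 24 | 1 (Week 36) |
| Week 36 | 0 |

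So the pooled column does not close uniformly at Week 24. However, every switcher who starts at Week 24 or 36 enters its denominator with fewer doses to withhold than a randomised BOTOX patient has.

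**Step 3: topiramate discontinuations after Week 24.** Two assumptions apply. The topiramate rate by Week 36 is p = 15%, and no BOTOX discontinuation is recorded after Week 24.

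*Constant hazard.* Rate by Week 24 = 1 − (1 − p)^(24/36) = 1 − 0.85^(2/3) = 10.3%. Unmatched part: 15.0 − 10.3 = 4.7 points.

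*Front-loaded stopping*, with the stopping rate halving every h weeks. Share after Week 24 = (2^(−24/h) − 2^(−36/h)) / (1 − 2^(−36/h)). The unmatched part is 15 × share.

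| h (weeks) | Share after Week 24 | Unmatched points |
|---|---|---|
| 24 | (0.500 − 0.354)/(1 − 0.354) = 22.7% | 3.4 |
| 12 | (0.250 − 0.125)/(1 − 0.125) = 14.3% | 2.1 |
| 8 | (0.125 − 0.044)/(1 − 0.044) = 8.5% | 1.3 |

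**Step 4: sensitivity to the assumed rate.** Under a constant hazard, the unmatched part is:

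| Rate by Week 36 | Rate by Week 24 | Unmatched points |
|---|---|---|
| 10% | 6.8% | 3.2 |
| 20% | 13.8% | 6.2 |
| 30% | 21.2% | 8.8 |

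If only 5% to 10% of stops fall after Week 24 and the 36-week rate is 10% to 30%, the range is 0.05 × 10 = 0.5 to 0.10 × 30 = 3.0 points.

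**The case against.** The strongest objections, and what stands of each:

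- **A Week 24 closure is nowhere stated.** The TEAE window and the BOTOX exposure definition both run to about Week 36. Protocol 8.8 requires a treatment-discontinuation form when BOTOX is stopped, with no Week 24 limit, so a site could record a withdrawal in Weeks 24-36. This stands. A reader might infer that the BOTOX measure simply shuts at Week 24, but the documents show only that the coding after Week 24 is undefined. That gap still needs a rule.
- **Only one measure is affected.** AE rates share the same nominal window, and Protocol 2.2 does not limit discontinuations to treatment discontinuations. This stands: the hypothesis as a whole does not compare unequal windows.
- **Study discontinuations due to AEs are tabulated too.** That table would catch a BOTOX patient who leaves in Weeks 24-36, but it has an asymmetry of its own. Under Protocol 8.8, patients who stop topiramate stay in the study and those who stop BOTOX exit. It does not restore a like-for-like comparison.
- **Early stopping is more plausible than a constant hazard**, given a 4-week titration and a last scheduled dose adjustment at Week 12 (Protocol 5.4.2). This is fair. It makes the front-loaded range the more natural one and 4.7 points an upper figure for a 15% rate.
- **The planned 36-week comparison is legitimate.** Late topiramate intolerance is real, and choosing between 24 and 36 weeks is a choice of estimand. This stands, and it argues for adding a common-window figure rather than replacing the planned one.
- **Relevant text may be redacted.** The protocol's safety measures and safety analyses and the SAP's endpoint section cannot be read, so a definition could lie there.

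**Conclusion.** The point holds in a limited form. As SAP 9.1.5 is visibly written, AE-related treatment discontinuation is a crude percentage set against unequal opportunities to stop. Those opportunities run to Week 36 on topiramate. For a patient randomised to BOTOX, no scheduled dose remains to be withdrawn after Week 24, and the coding of later AE exits is undefined. Pooling switchers into the BOTOX column blurs the comparison further. Any resulting bias in the randomised comparison would favour BOTOX.

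The size cannot be determined from the documents. It is about 1.3 to 3.4 points for front-loaded stopping and up to 4.7 points for a constant hazard. Both figures depend on the assumed 15% rate and on no BOTOX discontinuation being recorded after Week 24.

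A reader might infer that a third of topiramate AE discontinuations lack a counterpart. One third is the share of calendar time; it is roughly the share of events only under a constant hazard, which the documents do not establish. Nor does the point touch any p-value, the gatekeeping sequence or the primary endpoint: the comparison is descriptive.

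**What to change.** Keep the as-treated 36-week table in SAP 9.1.5 and add:

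1. A between-arm summary by randomised arm of AE-related treatment discontinuation up to and including the Week 24 visit, when the last BOTOX dose is given or withheld. Show later topiramate discontinuations and later BOTOX AE-related exits on separate rows.
2. A summary by randomised arm of all AE-related discontinuations of treatment or study up to Week 36, with an explicit rule for classifying a BOTOX AE exit after Week 24.

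State that the discontinuation part of the tolerability hypothesis will be read from these alongside the existing table. Grouping by randomised arm departs from the as-treated rule for safety tables, so the SAP should say so and give the reason: it keeps switchers out of the BOTOX comparison.

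The cost is SAP wording and one or two extra tables from dates already recorded. No treatment or visit changes. The common-window difference may be less favourable to BOTOX than the planned figure.
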